### **3.2.2 Intention to Treat (ITT) Population**

The population for this analysis will be all subjects who met the inclusion and exclusion criteria at screening, and were randomized. Subjects that meet inclusion and exclusion criteria and were randomized but have low baseline QIDS-SR scores will be included in ITT analysis.

### **3.3 Covariates**

Baseline HAM-D17 score is a covariate for the primary analysis. For secondary and exploratory analyses, the following covariates may be added to the model with baseline score: Age, Gender, Treatment, and Site Type (PCP/Psych).

### **3.4 Missing Data**

Missing observations of response variables will be checked and missing patterns by treatment and overall will be described including a CONSORT trial flow diagram. Missing values will be handled by using maximum likelihood method (ML). Complete cases analyses will be conducted and results will be compared to those obtained from ML. The main analysis conclusion at Week 8 will be drawn using ML method for the PP population (see Section 5.1).

## **4 SUMMARY OF STUDY DATA**

All continuous variables will be summarized using the following descriptive statistics: (non-missing) sample size (n), mean or median, standard deviation or range (maximum and minimum).

All categorical variables will be summarized using the frequency and percentage (based on the non-missing sample size) for each observed category.

All summary tables will be structured with a column showing the appropriate summary statistics for all participants combined, separate columns for Treatment As Usual (TAU), GeneSight (GEN), and Enhanced GeneSight (E-GEN) groups; sample sizes and/or numbers of missing observations will also be reported. A final column will show, where appropriate, estimates of effect size with their 95% confidence intervals.

Separate tables will be provided for the PP and ITT analyses.

### **4.1 Demographic and Baseline Variables**

Summary statistics for demographic and baseline variables will be produced and group differences will be computed for these variables.

## **5 EFFICACY ANALYSIS**

### **5.1 Primary Efficacy Analysis**

The primary measure of efficacy is the percentage change from baseline to week 8 in HAM-D17. The percentage change from baseline in HAM-D17 will be analyzed using a Mixed Model for Repeated Measures (MMRM). The model will include treatment, week (4 & 8), treatment-by-week interaction, baseline HAM-D17 score, baseline HAM-D17-by-week interaction as fixed effects. Unstructured covariance between measurements at weeks four and eight, from the same patient, will be incorporated into the model. If there is a convergence issue, Toeplitz covariance will be used. The MMRM method employed here is known as Maximum Likelihood (ML) to effectively handle the missing values as discussed in Section 3.4. The p-value will be derived from the T-test for comparing two treatment arms at week 8 (treatment by week interaction term). If overwhelming evidence suggests that the normality assumption is not satisfied, complete case analyses (CCA) of the primary efficacy endpoint will be conducted for the PP population for the completers of week eight. The primary endpoint will be analyzed by fitting an analysis of covariance (ANCOVA) model which includes baseline HAMD-17 score. Robust regression method (M Estimation Method by Huber) will be used for CCA to detect potential outliers and appropriately weigh the influence of the outliers should they exist.

As a sensitivity analysis, complete case analyses (CCA) of the primary efficacy endpoint will be conducted for the PP population for the completers of Week 8. The primary endpoint will be analyzed by fitting an analysis of covariance (ANCOVA) model which includes treatment, baseline HAMD-17 score, age, and gender. If age and gender are not statistically significant, they may be dropped from the final model. Robust regression method (M Estimation Method by Huber) will be used for CCA to detect potential outliers and appropriately weigh the influence of the outliers should they exist.

The above MMRM and CCA analyses will also be conducted for the ITT population.

The primary methods for checking the normality assumption will be through graphical assessment using a Q-Q plot and histogram of the residuals. If the points for the Q-Q plot are approximately linear and if the histogram is approximately bell-shaped, the residuals will be considered normally distributed.

The constant variance assumption will be checked by a scatter plot of residuals vs. predicted mean of response variable.

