10.0 SAMPLE SIZE

The study will recruit participants from approximately 8-12 sites stratified into 2 clusters. CAMH will constitute one study site and a single stratified cluster. The remaining sites will constitute the second cluster. The sample size required for this study was calculated using effect size estimates drawn from a previous study conducted by Hall-Flavin et al.(11) Assuming an effect size of 0.30 in HAM-D₁₇ score favoring the treatment group, intra class coefficient between clusters of 20%, statistical power of 90%, an alpha level of 0.05, and an expected 16.7% rate of premature discontinuation (based on ongoing studies and experience with the intervention) by Week 8 (primary endpoint), a total of 570 participants (i.e., 190 per treatment arm) are required to detect the same effect in this study. Sample size calculations were determined using SAS (SAS Institute, Inc., Version 9.3, Cary, NC).

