12.0 METHODS: ASSIGNMENT OF INTERVENTIONS

12.1 Allocation

12.1.1 Sequence Generation

Participants will be randomly assigned to one of the three treatments arms with a 1:1:1 allocation as per a computer generated randomization schedule stratified by site using permuted blocks of random sizes. The block sizes will not be disclosed, to ensure concealment.

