16.1.2 Diagnostics

Prior to formal statistical analyses, diagnostics will be conducted to determine appropriate statistical models. The independence assumption of ANOVA will be tested by examining the correlation between error terms for each dependent variable across levels of the indicator variable. To this end, the Durbin-Watson test statistic will be used to determine if the independence assumption was upheld. Values approaching 2.0 from the left or right were considered to be an indication of independence. The normality assumption will be tested by plotting residuals against the normal probability plot and by deriving the Shapiro-Wilk (S-W) test statistic. The dependent variable will formally be considered to be non-

normally distributed if the p-value for the S-W test was < 0.05 . Homogeneity of variance will be tested by employing the statistic derived by Brown and Forsythe. If the associated p-value for the test statistic is < 0.05 , then the dependent variable will be assumed to exhibit non-constant variance. If a given dependent variable did not meet the above mentioned assumptions (e.g., clustering due to study site), generalized estimating equations (GEEs) will be employed to account for the lack of independence between outcomes using an autoregressive correlation structure and identity link function.

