### **5.2 Secondary & Exploratory Efficacy Analyses**

The secondary analyses will be conducted using MMRM method for continuous response variables and ANCOVA with robust regression for complete cases for the PP population and may also be conducted for the ITT population.

As a secondary analysis, the following covariates will be added to the primary endpoint model with baseline score and analyzed the same way: treatment, age, gender, site type, and race included in the model. If covariates are not statistically significant, they may be dropped from the final model.

The secondary and exploratory measures of efficacy including percentage change from baseline in HAM-D6, QIDS-SR16, PHQ-9, GAD-7, CGI-S, change in EuroQol (EQ-5D-5L), and change in SF-36 will be analyzed the same way as for the primary efficacy variable above with baseline score included in the model. The secondary measures of efficacy will also be analyzed with baseline score, treatment, gender, site type, age, and race included in the model. If covariates are not statistically significant, they may be dropped from the final model.

Percentage of responders for HAM-D17, HAM-D6, QIDS-SR16, PHQ-9, GAD-7, CGI-S, CGI-I, CGI-EI, and SF-36, and remitters for HAM-D17, HAM-D6, QIDS-SR16, PHQ-9, GAD-7, and CGI-S will be analyzed by visit, separately, using a Generalized Linear Mixed model. Pre-specified covariates may be added.

Percentage of patients on congruent and incongruent medications will be compared between GEN and TAU using Chi-square tests at each time point.

Medication compliance using BARS and prescription filling data will be summarized and compared between treatment groups (see 7.6 for description).

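### Randomisation is stratified by site, but the primary MMRM and its fallback and sensitivity ANCOVAs have no site term, which costs some reported precision and power

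*SAP*

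**What the plan says.** Protocol 12.1.1 allocates patients 1:1:1 "as per a computer generated randomization schedule stratified by site using permuted blocks of random sizes". The synopsis (1.4) also names the outpatient treatment site as the stratification factor, and section 10.0 expects about 8-12 sites.

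SAP 5.1 defines the primary model: "The model will include treatment, week (4 & 8), treatment-by-week interaction, baseline HAM-D17 score, baseline HAM-D17-by-week interaction as fixed effects". The only covariance it specifies is within patient, between Weeks 4 and 8. If normality clearly fails, the fallback is a complete-case ANCOVA for which only baseline HAM-D17 is listed. The sensitivity analysis is an "analysis of covariance (ANCOVA) model which includes treatment, baseline HAMD-17 score, age, and gender". SAP 3.3 agrees: "Baseline HAM-D17 score is a covariate for the primary analysis".

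The nearest term elsewhere is site type (primary care or psychiatry), in the secondary and exploratory models of SAP 3.3 and 5.2. There, "If covariates are not statistically significant, they may be dropped from the final model". The responder and remitter endpoints "will be analyzed by visit, separately, using a Generalized Linear Mixed model", with no random effect named.

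Protocol 16.1.2 did mention site. Where model assumptions failed, with the example of "clustering due to study site), generalized estimating equations (GEEs) will be employed to account for the lack of independence between outcomes". SAP 1.2 states that the SAP replaces the protocol's analysis plan, and the SAP carries over no handling of site.

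**The concern.** Permuted blocks within site keep the arms close to balanced at each site, so a site with generally better or worse outcomes contributes about equally to both arms. The treatment difference is therefore largely free of between-site variance. A model that does not know about site still estimates its residual variance from all patients pooled, between-site differences included. Its standard error then describes a less precise design than the one that was run.

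At stake is the chance of detecting a real GEN effect, and the width of the interval that a reader or payer will see. The validity of a positive result is not at stake, because the error is in the conservative direction.

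Site type does not close the gap. It has two levels, is not the factor used in the randomisation, does not enter the primary model, and may be removed on a significance test.

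**Working it through.** **Inputs from the documents.** Effect size 0.30, 90% power, alpha 0.05, 16.7% discontinuation by Week 8, 190 per arm (Protocol 10.0); two-sided test (SAP 6).

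**Input not in the documents.** The share *v* of outcome variance between sites. The 20% intraclass coefficient in Protocol 10.0 refers to two groupings: "CAMH will constitute one study site and a single stratified cluster. The remaining sites will constitute the second cluster". It is not a between-site figure, so *v* is treated as an assumption and varied from 0 to 20%.

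**The plan's own figure.** Two-sided, equal arms: n = 2(1.960 + 1.282)²/0.30² = 233.5, so 234 per arm, and 234/0.833 gives 281 after dropout. With 20% of the variance removed, n = 0.8 × 233.5 = 186.8, so 187, and 187/0.833 gives 225 after dropout. A one-sided test without that removal needs 191, or 230 after dropout. The stated 190 is matched only when dropout is ignored (187 two-sided with the variance removed, or 191 one-sided). So 570 does not reproduce from its stated inputs. That is a separate matter, but the two-sided match needs between-cluster variance to be removed, and the SAP's primary model does not do this.

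**Effect of leaving site out.** Completers per arm: 190 × (1 − 0.167) = 158. Total SD is set to 1 and balance within site is taken as exact.

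- Reported SE without site: √(2/158) = 0.1125.
- True SE: 0.1125 × √(1 − v).
- Reported over true SE: 1/√(1 − v).
- Type I error without site: 2Φ(−1.96/√(1 − v)).
- Power without site: Φ((0.30√79 − 1.96)/√(1 − v)), with 0.30√79 = 2.666.
- Power with site: noncentral t, noncentrality 2.666/√(1 − v), df = 2 × 158 − 2 − 9 = 305 for 10 sites.

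| Site share v | Reported SE too large by | Type I error without site | Power without site | Power with site |
|---|---|---|---|---|
| 0% | 0% | 5.0% | 76.0% | 75.7% |
| 5% | 2.6% | 4.4% | 76.6% | 77.9% |
| 10% | 5.4% | 3.9% | 77.2% | 80.0% |
| 20% | 11.8% | 2.8% | 78.5% | 84.4% |

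**Simulation with imperfect balance.** 20,000 trials per value of *v*; 570 patients randomised 1:1:1 in blocks of 3, 6 or 9 within 10 sites (one holding 30% of patients); 16.7% random dropout; two arms compared at one time point.

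| Site share v | Type I without / with site | Power without / with site | Mean reported SE without site / SD of estimate |
|---|---|---|---|
| 0% | 4.8% / 4.8% | 75.6% / 75.4% | 0.1124 / 0.1117 |
| 5% | 4.8% / 5.2% | 75.8% / 77.3% | 0.1124 / 0.1113 |
| 10% | 3.8% / 4.8% | 77.1% / 80.2% | 0.1124 / 0.1066 |
| 20% | 3.3% / 5.1% | 77.9% / 84.5% | 0.1124 / 0.1030 |

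The mean estimate was 0.299 to 0.301 throughout, so there is no bias. Monte Carlo error is about 0.3 points on power and 0.15 on type I error. The small SE excess at 0% is simulation noise; the theoretical value is zero. With 8 and 12 sites at 20% (10,000 runs each), power was 78.2% versus 84.8% and 77.1% versus 83.6%.

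**Smaller per-protocol set.** SAP 3.2.1 makes the per-protocol set primary. If 130 per arm qualified (an assumption), the formulas give 68.1% versus 69.6% at 5%, 68.6% versus 71.9% at 10%, and 69.6% versus 76.9% at 20%.

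**The case against.** The strongest reply is that little is lost. A positive result stays valid, and at a 5% site share the gain is only about 1.3 points of power. The share may well be low, because HAM-D17 is scored by one or two central raters (Protocol 13.0) and baseline score is already in the model. The larger gains come from the 10% and 20% rows, which no document supports. All of this stands. It limits the size of the point but does not remove it, since central rating controls rater differences and not differences in case mix or prescribing across hospital clinics, family health teams and primary care (Protocol 6.1).

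It is also fair to say that the estimator loses almost no precision, because blocking has already secured it; what is wrong is the reported standard error. The protocol's GEE provision was conditional, gave site clustering as an example only, and specified an autoregressive structure, so the SAP dropped a fallback and not a firm site adjustment. The calculations use one time point and no baseline covariate, so they approximate the MMRM. Site may be the intended random effect in the responder models, but the SAP does not say so.

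**Conclusion.** The concern holds. The primary model and both supporting ANCOVAs omit the factor used to stratify the randomisation, and nothing else in the SAP takes its place. The result is a conservative test and an interval wider than the design warrants, without bias or excess false positives.

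The cost in power is nil at a zero site share, about 1 point at 5%, 3 points at 10% and 6 points at 20%. These figures assume an effect of 0.30, 158 completers per arm and near-balance within site. Per-protocol exclusions loosen that balance and would reduce the SE discrepancy somewhat. The omission is certain; its size is not, because no between-site variance is given. The change is still worth making: on the protocol's own effect size and dropout, two-sided power is about 76% against the 90% stated, and the possible gain far exceeds the possible loss.

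**What to change.** Before unblinding, amend SAP 5.1 and 3.3 to:

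- Add site, as a fixed effect or random intercept, to the primary MMRM and to the fallback and sensitivity ANCOVAs, for both the per-protocol and ITT populations.
- State whether site is crossed with week in the MMRM. A main effect alone assumes the same site differences at Weeks 4 and 8.
- Keep site whatever its p-value, exempting it from the rule that allows non-significant covariates to be dropped.
- Set a minimum size below which sites other than CAMH are pooled.
- In SAP 5.2, name site as the random effect or a covariate in the responder and remitter models, and note that the odds ratio is then conditional on site.

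No new data are needed. The costs are up to about 11 degrees of freedom with 12 sites (more if site is crossed with week), about 0.3 points of power if the site share is zero, a pooling rule to write, and odds ratios that are conditional and not marginal.

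### SAP 5.1 lets a visual normality check, with no threshold, send the primary endpoint to a completers-only Huber ANCOVA; it must be reconciled with SAP 3.4, and the remedy does not fit the trigger

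*SAP*

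**What the plan says.** SAP 5.1 analyses percentage change in HAM-D17 with an MMRM on Weeks 4 and 8. Its terms are treatment, week, baseline and their interactions with week, and likelihood estimation deals with missing values. The p-value comes from the Week 8 treatment contrast.

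The same paragraph continues: "If overwhelming evidence suggests that the normality assumption is not satisfied, complete case analyses (CCA) of the primary efficacy endpoint will be conducted". That step is restricted to Per Protocol patients who completed Week 8. The model for this step is an "analysis of covariance (ANCOVA) model which includes baseline HAMD-17 score", and "Robust regression method (M Estimation Method by Huber) will be used for CCA". Normality is assessed graphically: "If the points for the Q-Q plot are approximately linear and if the histogram is approximately bell-shaped", the residuals count as normal. No test, cut-off or assessor is named, and nothing is said about whether the check is blinded.

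The next paragraph of 5.1 plans a completer ANCOVA with Huber weighting unconditionally, as a sensitivity analysis. That model lists treatment, baseline, age and gender. MMRM and completer analyses are also to be run in the ITT population.

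SAP 3.4 states: "The main analysis conclusion at Week 8 will be drawn using ML method for the PP population", and refers the reader to 5.1.

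**The concern.** A plan should fix which analysis gives the primary result. Here a step that depends on a subjective look at residuals sits inside the primary-analysis paragraph, and another section names ML without qualification. Two statisticians could follow this SAP in good faith and report different primary results.

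The remedy also does not address the problem that triggers it. Non-normal residuals affect how well the reference distribution approximates the truth, which matters little for a mean contrast at this sample size. The fallback instead changes three other things:

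- It discards patients who have a Week 4 but no Week 8 value.
- It replaces an assumption that missingness may depend on baseline, arm and Week 4 with one that it depends on baseline and arm only.
- Through Huber weighting, it moves the target away from the mean percentage change named in the hypothesis of SAP 2.1.1.

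SAP 5.2 analyses the continuous secondary endpoints in the same way as the primary, so the ambiguity carries over to them.

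**Working it through.** **Does the text replace the MMRM or add to it?** The conditional and unconditional completer analyses use the same patients and the same weighting. They differ only in the listed covariates: the sensitivity model has treatment, age and gender in addition to baseline, and age and gender may be dropped if not significant. What is then left is treatment plus baseline. The conditional sentence therefore adds almost nothing unless it changes which result is primary. SAP 3.4 points the other way but refers back to the section that holds the fallback. The text does not settle the matter.

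**Size of the possible bias.** The plan gives no figure to reproduce. Inputs from Protocol 10.0: 190 per arm and 16.7% discontinuation by Week 8, so 190 × (1 − 0.167) ≈ 158 completers per arm. Assumed, because the documents give neither: Week 4/Week 8 correlation ρ of 0.4–0.8, and a logistic slope b of 0.3–1.0 for dropout on the standardised Week 4 score. All dropout is taken to occur after Week 4.

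1. Dropout probability p(x) = 1/(1 + exp(−(a + bx))), with a set so that mean p = 0.167. The completers' mean Week 4 score moves by m(b) = 0.0495, 0.109 and 0.147 SD for b = 0.3, 0.7 and 1.0.
2. Shift s in the Week 8 contrast: ρ·m if the mechanism acts in one arm, 2ρ·m if it is opposite by arm, and 0 under no treatment effect if it is shared.
3. SE = √(2/158) = 0.1125 SD. Two-sided type I error = Φ(−1.96 + s/SE) + Φ(−1.96 − s/SE).

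| b | ρ | One arm: s, type I error | Opposite: s, type I error |
|---|---|---|---|
| 0.3 | 0.4 | 0.020, 5.4% | 0.040, 6.4% |
| 0.7 | 0.65 | 0.071, 9.7% | 0.142, 24.4% |
| 1.0 | 0.8 | 0.117, 18.1% | 0.234, 54.9% |

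Simulation over the same grid gave 0.02–0.12 SD (about 5–18%) and 0.03–0.24 SD (about 6–56%), so the two methods agree to within about 0.01 SD.

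**Losses before Week 4.** These patients have no outcome in either analysis. Suppose half are lost at random before Week 4 (assumed). Dropout related to Week 4 score is then 0.0835/0.9165 = 9.1% of those remaining. At b = 0.7 and ρ = 0.65 the shifts are 0.040 and 0.079 SD, with type I error of about 6.5% and 11%.

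**MMRM against the Huber completer ANCOVA.** A separate simulation used 190 randomised per arm, 4,000 runs per scenario, ρ of 0.5 and 0.7, dropout slope 1 where it depends on Week 4 score, and a true effect of 0.30 SD where there is one.

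- MMRM: type I error 4.7–5.9%, estimate 0.30, power about 77–80%.
- Completers, random dropout or a shared mechanism: estimate 0.285–0.30, power about 72–75%.
- Completers, mechanism in one arm: shift about 0.08–0.115 SD, type I error 10.5–18%.
- Completers, opposite by arm: shift about 0.15–0.20 SD, type I error 25–43%.
- Skewed errors, shared mechanism: MMRM remained unbiased with type I error of 5.5%.

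MMRM is unbiased here because dropout was generated to depend on observed Week 4 data.

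**The case against.** The SAP never says that the completer analysis takes the MMRM's place. It ties the p-value to the MMRM contrast, and SAP 3.4 can be read as settling the question in favour of ML. A reader might infer that the primary p-value is formally free to come from either analysis; the text supports an ambiguity, with replacement as the more natural reading, and no more.

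Other strong inferences also go too far:

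- **That the switch would be made on unblinded results.** The SAP does not say whether the residual check is blinded, and a pooled Q-Q plot does not itself show the treatment difference.
- **That percentage change is bound to look skewed, so the trigger will fire.** Improvement is capped at 100% and worsening is not, so skew is plausible. But the PP set requires a baseline HAM-D17 of at least 14 (SAP 3.2.1), which removes the smallest denominators, and the stated bar is overwhelming evidence.
- **That type I error would take one particular inflated value.** The error rates apply only if the trigger fires and dropout works differently by arm. No probability can be given for either.
- **That the fallback is meant to omit treatment.** The hypothesis is GEN versus TAU and the sensitivity model lists treatment, so this is probably a drafting slip.

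Two further points stand. SAP 3.2.1 lists a Week 8 visit 48–64 days after baseline; if that requires the visit, the PP set is already close to completers and the switch changes little there. And both analyses would be reported in PP and ITT, so a switch could be seen. Nor is Huber weighting unreasonable in itself: with skewed errors its power matched the MMRM's (78.6% against 78.5%). That supports it as a sensitivity analysis, but is no reason to drop incomplete patients.

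**Conclusion.** The point holds as an ambiguity over which analysis is primary, joined to a remedy that does not match its trigger. SAP 5.1 and 3.4 must be reconciled.

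The possible harm runs from negligible to large, and the documents cannot place it within that range. With all dropout after Week 4 and related to Week 4 score, the completer contrast shifts by 0.02–0.12 SD if the mechanism acts in one arm and by 0.03–0.24 SD if it is opposite by arm. The planned effect is 0.30 SD. Bias is negligible with a shared mechanism (at most about 0.015 SD), smaller when some losses precede Week 4, and small in PP if a Week 8 visit is already required. The ITT analysis stays exposed in every case. Mechanisms that differ by arm are possible because treating clinicians know the allocation (Protocol 13.0), but nothing in the documents shows that they occur.

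This should be corrected because the correction costs almost nothing, not because serious bias has been demonstrated.

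**What to change.** In SAP 5.1, state that the MMRM Week 8 contrast is the primary analysis whatever the residual plots show, and delete the conditional move to completers. If residuals look non-normal, report a sandwich or bootstrap confidence interval for that same contrast. Keep the Huber completer ANCOVA as a sensitivity analysis only, with treatment listed in the model. SAP 3.4 then agrees with 5.1 as it stands. The cost is a few lines of SAP wording and one bootstrap run; no change to data collection or sample size is needed.
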